10.5.2.3. Handling of Missing Data for Statistical Analysis

Missing data will remain missing with no imputation applied for the purposes of statistical analysis.

10.6. Appendix 6: Values of Potential Clinical Importance

10.6.1. Laboratory Values

Haematology				
Laboratory Parameter	Units	Category	Clinical Concern Range	
			Low Flag (< x)	High Flag (>x)
Hematocrit	Ratio of 1	Male		0.54
		Female		0.54
		Δ from BL	↓0.075	
Hemoglobin	g/L	Male		180
		Female		180
		Δ from BL	↓25	
Lymphocytes	x10 ⁹ / L		0.8	
Neutrophil Count	x10 ⁹ / L		1.5	
Platelet Count	x10 ⁹ / L		100	550
White Blood Cell Count (WBC)	x10 ⁹ / L		3	20

Clinical Chemistry				
Laboratory Parameter	Units	Category	Clinical Concern Range	
			Low Flag (< x)	High Flag (>x)
Albumin	mmol/L		30	
Calcium	mmol/L		2	2.75
Creatinine	mmol/L	Δ from BL		↑ 44.2
Glucose	mmol/L		3	9
Magnesium	mmol/L		0.5	1.23
Phosphorus	mmol/L		0.8	1.6
Potassium	mmol/L		3	5.5
Sodium	mmol/L		130	150
Total CO ₂	mmol/L		18	32

Liver Function				
Test Analyte	Units	Category	Clinical Concern Range	
ALT/SGPT	U/L	High	≥ 2x ULN	
AST/SGOT	U/L	High	≥ 2x ULN	
AlkPhos	U/L	High	≥ 2x ULN	
T Bilirubin	μmol/L	High	≥ 1.5xULN	
T. Bilirubin + ALT	μmol/L U/L	High	1.5xULN T. Bilirubin + ≥ 2x ULN ALT	

10.6.2. Vital Signs

Vital Sign Parameter (Absolute)	Units	Clinical Concern Range	
		Lower	Upper
Systolic Blood Pressure	mmHg	< 85	> 160
Diastolic Blood Pressure	mmHg	< 45	> 100
Heart Rate	bpm	< 40	> 110

Vital Sign Parameter (Change from Baseline)	Units	Clinical Concern Range			
		Decrease		Increase	
		Lower	Upper	Lower	Upper
Systolic Blood Pressure	mmHg	≥ 20	≥ 40	≥ 20	≥ 40
Diastolic Blood Pressure	mmHg	≥ 10	≥ 20	≥ 10	≥ 20
Heart Rate	bpm	≥ 15	≥ 30	≥ 15	≥ 30

10.7. Appendix 7: Model Checking and Diagnostics for Statistical Analyses

10.7.1. Statistical Analysis Assumptions

Endpoint(s)	
• Proportion of flow cytometry cell counts
Analysis	
• GLMM

• Model assumptions will be applied, but appropriate adjustments maybe applied based on the data.• The Kenward and Roger method for approximating the denominator degrees of freedom and correcting for bias in the estimated variance-covariance of the fixed effects will be used.• An unstructured covariance structure for the R matrix will be used by specifying 'type=UN' on the RANDOM line.
○ In the event that this model fails to converge, alternative correlation structures may be considered such as CSH or CS.○ Akaike's Information Criteria (AIC) will be used to assist with the selection of covariance structure.• Distributional assumptions underlying the model used for analysis will be examined by obtaining a normal probability plot of the residuals and a plot of the residuals versus the fitted values (i.e. checking the normality assumption and constant variance assumption of the model respectively) to gain confidence that the model assumptions are reasonable.• If there are any departures from the distributional assumptions, alternative models will be explored using appropriate transformed data.	

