8.2.2. Sample Size Sensitivity

No formal sample size sensitivity analysis has been performed.

The precision for iLN estimates is expected to be lower than the precision for PBMC estimates, since it is anticipated that fewer cells will be available from iLN biopsies for flow cytometry analysis. No published data was found for the phenotypes of interest in iLN biopsies.

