8.4. Key Elements of Analysis Plan

8.4.1. Primary Analyses

Descriptive statistics will be calculated for each of the primary flow cytometry cell types by group and sample type (blood / core biopsy / fine needle aspirate biopsy). The flow cytometry data for each cell type will be displayed graphically using scatter plots of cell count and % cell count versus group and/or sample type.

Generalized linear models with appropriate link functions will be used to analyze data separately for each flow cytometry cell type. Models will include terms for group, sample type, and the interaction of group with sample type. Subject will be included as a random effect term.

- For absolute cell counts, these models will estimate the mean cell count for each sample type in each group, comparing means as outlined in the primary hypothesis section.
- For proportional cell counts, these models will estimate the average odds (or relative risk) of having a particular cell type for each sample type in each group, comparing these odds (or relative risks) by estimating the ratios for the primary comparisons of interest.

All estimates will be presented with 95% confidence intervals.

Model assumptions will be checked, and modifications to the model or alternative approaches may be considered in the event of significant deviations from model assumptions.

Further details will be provided in the Reporting and Analysis Plan (RAP).

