7. PRIMARY STATISTICAL ANALYSES

7.1. Biomarker Analyses

7.1.1. Overview of Planned Biomarker Analyses

The primary biomarker analyses will be based on the ‘Safety’ population, unless otherwise specified.

Between group (HV vs NOT1D) comparisons will use data from all subjects who have at least one evaluable sample from either method. Between method comparisons and analyses will only be performed in subjects who provide sufficient cells from both methods in each pairwise comparison (as shown in [Figure 1](#)).

If sufficient numbers of cells to meet the cell number requirements of the primary endpoint are obtained by both biopsy methods, the primary endpoint analysis will be carried out independently for each biopsy method, otherwise only the biopsy method for which sufficient numbers of cells were obtained will be used for primary analysis.

Details of the planned displays are presented in [Appendix 10: List of Data Displays](#)

For biomarkers that indicate a difference between methods or groups, further explanatory analyses may be carried out to explore correlations between biomarkers or the impact of covariates.

7.1.1.1. Interim Analyses 1

Summary statistics and a listing for the overall cell counts will be presented.

7.1.1.2. Interim Analyses 2

All primary and secondary comparisons will be presented, as detailed in [Appendix 10: List of Data Displays](#)

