7.1.2. Planned Biomarker Statistical Analyses

Primary Statistical Analyses
Endpoint(s)

 • Proportion of flow cytometry cell counts
Model Specification

 • Endpoints analyzed for each flow cytometry cell type using generalized linear mixed models (GLMM). 
The analysis will be performed on the parameters listed in
 
 • Appendix 8: Biomarker Analyses • Terms in GLMM model will include: 
 Fixed categorical: group, sample type, and the interaction of group with sample type Random effect: subject Where group is either HV or NOT1D, and sample type is peripheral blood, core biopsy or fine needle aspirate.
Model Checking & Diagnostics

Refer to
 
 • Appendix 7: Model Checking and Diagnostics for Statistical Analyses
Model Results Presentation

 • For proportional cell counts, these models will estimate the mean (or geometric mean) proportion for each sample type in each group, comparing means using differences or ratios as outlined in the primary hypothesis section.

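### Does asking for both a subject random effect and an unstructured R matrix make the biomarker model unusable?

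*SAP*

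**What the plan says.** Protocol 8.4.1 gives generalized linear models with group, sample type and their interaction, and states "Subject will be included as a random effect term". Final SAP 7.1.2 repeats this: "Fixed categorical: group, sample type, and the interaction of group with sample type", with "Random effect: subject", where "sample type is peripheral blood, core biopsy or fine needle aspirate".

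Final SAP 10.7.1 sets out the covariance: "An unstructured covariance structure for the R matrix will be used by specifying 'type=UN' on the RANDOM line". It then gives a fallback: "In the event that this model fails to converge, alternative correlation structures may be considered such as CSH or CS". AIC is to help with the choice, and Kenward-Roger degrees of freedom are specified. The planned diagnostics check normality and constant variance of the residuals.

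For comparisons between sampling methods, final SAP 7.1.1 says "Between method comparisons and analyses will only be performed in subjects who provide sufficient cells from both methods in each pairwise comparison".

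The RANDOM statement is not written out in full, and no distribution or link is named. Neither document says whether the unstructured matrix stands in for the subject intercept or is added to it. The SAP for the second interim analysis has the same pair of statements.

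**The concern.** Read literally and together, sections 7.1.2 and 10.7.1 ask for two descriptions of the same within-subject correlation. In a normal model with one observation per subject and sample type, they cannot be separated. The covariance-parameter Hessian is then singular, and software may issue warnings or stop.

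If an analyst treats that as failure to converge, the fallback is triggered for a reason unrelated to the data. This could happen separately in each of the 70 leukocyte-subset models (22 + 30 + 18 parameters in final SAP 10.8.2.1 to 10.8.2.3), so different subsets might be reported under different structures. The study reports estimates with 95% confidence intervals and tests no hypotheses, so doubt about the covariance is doubt about its main output.

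**Working it through.** **Inputs.** There are three sample types (final SAP 7.1.2). Each gives one value per subject: cores are pooled and aspirates are pooled (final SAP 10.8.1), and one blood sample is taken (Blood population, final SAP section 4). There are at most 15 subjects per group (Protocol 8.2). The documents give no variances, so those used below are illustrative.

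**Counting parameters.** Write the within-subject covariance as V = τ²·11′ + R, where τ² is the subject variance. With k sample types, V has k(k+1)/2 distinct elements: 3×4/2 = 6 for three types and 2×3/2 = 3 for two. The rank is that of the derivative of V with respect to the parameters.

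| Structure for R, subject intercept kept | Three types: parameters / rank | Two types: parameters / rank |
|---|---|---|
| UN | 6 + 1 = 7 / 6 | 3 + 1 = 4 / 3 |
| CSH | 4 + 1 = 5 / 5 | 3 + 1 = 4 / 3 |
| CS | 2 + 1 = 3 / 2 | 2 + 1 = 3 / 2 |

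UN with no intercept has 6 parameters and rank 6 for three types, and 3 and 3 for two. The redundancy is therefore real for UN and CS. CSH, the fallback named first, is identifiable with three types. It is weakly determined there: the smallest singular value was 0.13 against a largest of 3.33.

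**What the redundancy does to the fit.** Only τ² + R enters the likelihood. For example, τ² = 0.2 with R₁₁ = 1.0 and R₁₂ = 0.3 gives V₁₁ = 1.2 and V₁₂ = 0.5. Setting τ² = 0 with R₁₁ = 1.2 and R₁₂ = 0.5 gives the same V. Two numerical checks, each on one simulated data set of 15 per group with three sample types, agree:

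- The maximised −2 log-likelihood is 218.994 at τ² = 0, 0.05, 0.1, 0.2 and 0.3, with R positive definite each time.
- −2REML is 88.110, and the group-difference standard errors are 0.260, 0.481 and 0.463, at τ² = 0, 0.1, 0.2 and 0.3.

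The likelihood is flat along one direction, and V, the estimates and their standard errors do not move along it. For UN, V is linear in the parameters and does not change in the redundant direction. A Kenward-Roger adjustment computed with a generalised inverse is therefore that of the UN model alone. The same argument shows that a subject intercept plus CS fits the same V as CS alone.

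**If the fallback is used without an intercept.** Choosing among UN, CSH and CS by AIC (2,500 simulated trials, 15 per group, SDs 1, 1.5 and 1.5 for blood and the two biopsy types) gave 95% interval coverage of 0.946, 0.948 and 0.942.

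**Does the text require both components?** Section 7.1.2 lists model terms. Section 10.7.1 says how their covariance is coded, and it speaks of one RANDOM line and of the R matrix. A single statement with subject as the clustering unit and an unstructured matrix over sample type satisfies both sections.

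**The case for a change.** The strongest opposing case is that the wording also allows UN to be attached to the single subject effect. That is a random intercept with one residual variance shared by blood, aspirate and core. Protocol 8.2.2 gives a reason to expect unequal variances: "The precision for iLN estimates is expected to be lower than the precision for PBMC estimates", because fewer cells will be available. With 15 per group and correlation 0.3, simulated coverage for HV versus NOT1D under that model (10,000 trials, Satterthwaite degrees of freedom) was:

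| Assumed iLN:blood SD ratio | Blood | iLN |
|---|---|---|
| 1 | 95% | 95% |
| 1.25 | 98% | 93–94% |
| 1.5 | 99% | 92% |
| 2 | 99.8% | 91% |

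The lymph-node intervals, which matter most here, would be too narrow. The arithmetic stands, but the reading does not. A covariance type applied to one scalar effect is not an unstructured R matrix. CSH and CS would also mean nothing as alternatives to it. The SD ratios are assumptions, since the documents report none.

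Three smaller points stand in part.

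- If an intercept is kept and the redundant parameter is counted, AIC for UN and CS rises by 2×1 = 2 relative to CSH. This disappears under the single-statement reading.
- At 5 per group and ratio 1.5, AIC chose CS in 54% of trials and iLN coverage was 93–94%. Those models had no intercept, so this reflects small numbers and data-driven selection, not the redundancy.
- Structures may differ between subsets. The planned fallback already permits that, and writing out the RANDOM statement would not remove it.

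The redundancy is exact only for a normal model, including one on transformed data. The planned residual checks imply such a model, although Protocol 8.4.1 allows other links. In an illustrative logit case with group means that differ, the rank was 7 of 7.

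**Conclusion.** The plan leaves a coding detail unstated, and an analyst settles it when writing the model. Fitting UN with a redundant subject intercept and fitting UN alone give the same covariance, estimates and confidence intervals, so the numerical effect on the planned UN analysis is nil. The remaining cost is possible Hessian or convergence warnings. No SAS fit was run and no non-convergence rate was computed, so their frequency is unknown; a singular Hessian is in any case not the same as failure to converge.

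This rests on a normal-type model, one value per subject and sample type, and section 10.7.1 meaning what it says about an unstructured R matrix. Writing out the RANDOM statement, distribution and link would be tidy, but it would not alter a reported result in this exploratory, estimation-only study. No change to the plan follows.

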10.8. Appendix 8: Biomarker Analyses

10.8.1. Frequency of Leukocytes

Test Analyte	Details
Core biopsy total cell number	Total number of cells obtained from pooled core biopsies
Fine Needle Aspirate total cell number	Total number of cells obtained from pooled fine needle aspirates

10.8.2. Frequency and phenotype of leukocyte subsets by flow cytometry

10.8.2.1. B_DC_Monocyte Panel

Test Analyte	Details
%DC (MNC)	NONCD16hiCD3-CD19-NK-HLADR+CD14-CD16- out of mono-nuclear cells
%Myeloid DC (DC)	NONCD16hiCD3-CD19-NK- HLADR+CD14-CD16-CD11C+CD123-
%pDC (DC)	NONCD16hiCD3-CD19-NK-HLADR+CD14-CD16-CD11C-CD123+
%Plasmablast (B)	NONCD16hiCD19+CD27+CD38+
%Circulating B (B)	NONCD16hiCD19+Plasmablast-CD27+IgD+
%Classical B (B)	NONCD16hiCD19+Plasmablast-CD27+IgD-
%Double neg B (B)	NONCD16hiCD19+Plasmablast-CD27-IgD-
%Naive B (B)	NONCD16hiCD19+Plasmablast-CD27-IgD+
%Transitional B (B)	NONCD16hiCD19+Plasmablast-CD27-IgD+CD38+CD24+
%CD56bright NK (NK)	NONCD16hiCD3-CD19- CD14- CD56hi CD16-
%CD56loCD16+ NK (NK)	NONCD16hiCD3-CD19- CD14- CD56lo CD16+
%CD56loCD16- NK (NK)	NONCD16hiCD3-CD19- CD14- CD56lo CD16-
%CD56+CD16+ NK (NK)	NONCD16hiCD3-CD19- CD14- CD56+ CD16+
% NK (MNC)	NONCD16hiCD3-CD19- CD14- out of mono-nuclear cells
%CD56bright NK (MNC)	NONCD16hiCD3-CD19- CD14- CD56h CD16-i out of mono-nuclear cells
%CD56loCD16+ NK (MNC)	NONCD16hiCD3-CD19- CD14- CD56loCD16+ out of mono-nuclear cells
%CD56loCD16- NK (MNC)	NONCD16hiCD3-CD19- CD14- CD56loCD16- out of mono-nuclear cells
%CD56+CD16+ NK (MNC)	NONCD16hiCD3-CD19- CD14- CD56+CD16+ out of mono-nuclear cells
%CD14+ monocyte (monocyte)	NONCD16hiCD3-CD19-NK-HLADR+Monocyte+CD14+
%CD14+CD16+ monocyte (monocyte)	NONCD16hiCD3-CD19-NK-HLADR+Monocyte+CD14+CD16+
%CD16+ monocyte (monocyte)	NONCD16hiCD3-CD19-NK-HLADR+Monocyte+CD16+
%B (MNC)	NONCD16hiCD19+ out of mono-nuclear cells

10.8.2.2. T Cell panel

Test Analyte	Details
%CD8 Tn (CD8)	CD3+CD4-CD45RA+CCR7+CD95-
%CD8 Tcm (CD8)	CD3+CD4-CD45RA-CCR7+
%CD8 Tem (CD8)	CD3+CD4-CD45RA-CCR7-
%CD8 Temra (CD8)	CD3+CD4-CD45RA+CCR7-
%CD8 Tscm (CD8)	CD3+CD4-CD45RA+CCR7+CD95+
%Tconv Tn (Tconv)	CD3+CD4+Treg-CD45RA+CCR7+CD95-
%TconvTcm (Tconv)	CD3+CD4+Treg-CD45RA-CCR7+
%Tconv Tem (Tconv)	CD3+CD4+Treg-CD45RA-CCR7-
%TconvTemra (Tconv)	CD3+CD4+Treg-CD45RA+CCR7-
%Tconv Tscm (Tconv)	CD3+CD4+Treg-CD45RA+CCR7+CD95+
%Tconv Th1 (mTconv)	CD3+CD4+Treg-Tconv Tn-Tconv Tscm-CXCR5-CXCR3+CCR4-CCR10-CCR6-
%Tconv Th1Th17 (mTconv)	CD3+CD4+Treg-Tconv Tn-Tconv Tscm-CXCR5-CXCR3+CCR4-CCR10-CCR6+
%Tconv Th1Th2 (mTconv)	CD3+CD4+Treg-Tconv Tn-Tconv Tscm-CXCR5-CXCR3+CCR4+CCR10-CCR6-
%Tconv Th1Th17Th2 (mTconv)	CD3+CD4+Treg-Tconv Tn-Tconv Tscm-CXCR5-CXCR3+CCR4+CCR10-CCR6+
%TconvTh2 (mTconv)	CD3+CD4+Treg-Tconv Tn-Tconv Tscm-CXCR5-CXCR3-CCR4+CCR10-CCR6-
%TconvTh17 (mTconv)	CD3+CD4+Treg-Tconv Tn-Tconv Tscm-CXCR5-CXCR3-CCR4+CCR10-CCR6+
%TconvTh22 (mTconv)	CD3+CD4+Treg-Tconv Tn- Tconv Tscm-CXCR5-CXCR3-CCR4+CCR10+CCR6+
%Tconv Tf _h (mTconv)	CD3+CD4+Treg-Tconv Tn-Tconv Tscm-CXCR5+
%Tconv PD-1+ ICOS+ Tf _h (mTconv)	CD3+CD4+Treg-Tconv Tn-Tconv Tscm-CXCR5+PD-1+ICOS+
%Treg Th1 (mTreg)	CD3+CD4+CD25+CD127loTreg Tn-Treg Tscm-CXCR5-CXCR3+CCR4-CCR10-CCR6-
%Treg Th1Th17 (mTreg)	CD3+CD4+CD25+CD127loTreg Tn-Treg Tscm-CXCR5-CXCR3+CCR4-CCR10-CCR6+
%Treg Th1Th2 (mTreg)	CD3+CD4+CD25+CD127loTreg Tn-Treg Tscm-CXCR5-CXCR3+CCR4+CCR10-CCR6-
%Treg Th1Th17Th2 (mTreg)	CD3+CD4+CD25+CD127loTreg Tn-Treg Tscm-CXCR5-CXCR3+CCR4+CCR10-CCR6+
%Treg Th2 (mTreg)	CD3+CD4+CD25+CD127loTreg Tn-Treg Tscm-CXCR5-CXCR3-CCR4+CCR10-CCR6-
%Treg Th17 (mTreg)	CD3+CD4+CD25+CD127loTreg Tn-Treg Tscm-CXCR5-CXCR3-CCR4+CCR10-CCR6+

Test Analyte	Details
%Treg Th22 (mTreg)	CD3+CD4+CD25+CD127loTreg Tn-Treg Tscm-CXCR5-CXCR3-CCR4+CCR10+CCR6+
%Treg Tfh (mTreg)	CD3+CD4+CD25+CD127loTreg Tn-Treg Tscm-CXCR5+
%Treg PD-1+ ICOS+ Tfh (mTreg)	CD3+CD4+CD25+CD127loTreg Tn-Treg Tscm-CXCR5+PD-1+ICOS+
%Tconv PD-1+ ICOS+ Tfh (Tconv Tfh)	CD3+CD4+Treg-Tconv Tn-Tconv Tscm-CXCR5+PD-1+ICOS+ out of Tconv Tfh
%Treg PD-1+ ICOS+ Tfh (Treg Tfh)	CD3+CD4+CD25+CD127loTreg Tn-Treg Tscm-CXCR5+PD-1+ICOS+ out of Treg Tfh

10.8.2.3. Treg panel

Test Analyte	Details
%CD15s+ Tconv (Tconv)	CD3+CD4+CD25lo-medFOXP3-CD15s+
%CD69+ Tconv (Tconv)	CD3+CD4+CD25lo-medFOXP3-CD69+
%Helios+ Tconv (Tconv)	CD3+CD4+CD25lo-medFOXP3-HELIOS+
%Ki67+ Tconv (Tconv)	CD3+CD4+CD25lo-medFOXP3-Ki67+
%CD15s+ mTconv (mTconv)	CD3+CD4+CD25lo-medFOXP3-CD45RA-CD15s+
%CD69+ mTconv (mTconv)	CD3+CD4+CD25lo-medFOXP3-CD45RA-CD69+
%Helios+ mTconv (mTconv)	CD3+CD4+CD25lo-medFOXP3-CD45RA-HELIOS+
%Ki67+ mTconv (mTconv)	CD3+CD4+CD25lo-medFOXP3-CD45RA-Ki67+
%Treg (CD4)	CD3+CD4+CD25hiFOXP3+
%aTreg (Treg)	CD3+CD4+CD25hiFOXP3hiCD45RA-
%mTreg (Treg)	CD3+CD4+CD25hiFOXP3medCD54RA-
%rTreg (Treg)	CD3+CD4+CD25hiFOXP3medCD45RA+
%CD15s+ Treg (Treg)	CD3+CD4+CD25hiFOXP3+CD15s+
%CD69+ Treg (Treg)	CD3+CD4+CD25hiFOXP3+CD69+
%Helios+ Treg (Treg)	CD3+CD4+CD25hiFOXP3+HELIOS+
%Ki67+ Treg (Treg)	CD3+CD4+CD25hiFOXP3+Ki67+
%CD69+ CD8 (CD8)	CD3+CD8+CD69+
%Ki67+ CD8 (CD8)	CD3+CD8+Ki67+

10.8.2.4. Ratios of effector cells to regulatory cells

The following parameters are derived.

Test analyte	Details
Th1 Tconv:Treg	Th1 Tconv cell to Treg cell ratio Derivation: [%Tconv Th1 (mTconv)] / [%Treg Th1 (mTreg)]
Th1Th17 Tconv:Treg	Th1Th17 Tconv cell to Th1Th17reg cell ratio

Test analyte	Details
	Derivation: [%Tconv Th1Th17 (mTconv)] / [%Treg Th1Th17 (mTreg)]
Th1Th2 Tconv:Treg	Th1Th2 Tconv cell to Th1Th2reg cell ratio Derivation: [%Tconv Th1Th2 (mTconv)] / [%Treg Th1Th2 (mTreg)]
Th1Th17Th2 Tconv:Treg	Th1Th17Th2 Tconv cell to Th1Th17Th2reg cell ratio Derivation: [%Tconv Th1Th17Th2 (mTconv)] / [%Treg Th1 Th17Th2 (mTreg)]
Th2 Tconv:Treg ratio	Th2 Tconv cell to Th2reg cell ratio Derivation: [%TconvTh2 (mTconv)] / [%Treg Th2 (mTreg)]
Th17 Tconv:Treg ratio	Th17 Tconv cell to T17reg cell ratio Derivation: [%TconvTh17 (mTconv)] / [%Treg Th17 (mTreg)]
Th22 Tconv:Treg ratio	Th22 Tconv cell to Th22reg cell ratio Derivation: [%TconvTh22 (mTconv)] / [%Treg Th22 (mTreg)]
Tfh Tconv:Treg ratio	Tfh Tconv cell to Tfhwreg cell ratio Derivation: [%Tconv Tfh (mTconv)] / [%Treg Tfhw (mTreg)]

10.8.2.5. Suppressive activity of regulatory cells

Test Analyte	Details
Percentage suppression 0:1	Treg: Tconventional cell ratio 0:1
Percentage suppression 1:2	Treg: Tconventional cell ratio 1:2
Percentage suppression 1:4	Treg: Tconventional cell ratio 1:4

10.8.2.6. General Derivations

For the parameters in Section 10.8.2.1, Section 10.8.2.2 and Section 10.8.2.3, the percentages will be transformed into counts by multiplying by the denominator counts / 100. The denominator counts are given in brackets in the test analyte column.

10.9. Appendix 9: Abbreviations & Trade Marks

10.9.1. Abbreviations

Abbreviation	Description
AE	Adverse Event
A&R	Analysis and Reporting
BL	Baseline
CI	Confidence Interval
CS	Clinical Statistics
CSR	Clinical Study Report
CTR	Clinical Trial Register
DOB	Date of Birth
DP	Decimal Places
eCRF	Electronic Case Record Form
FNA	Fine needle aspirate
HV	Healthy volunteer
IA	Interim Analysis
ICH	International Conference on Harmonisation
IDSL	Integrated Data Standards Library
iLN	Inguinal lymph node
IMMS	International Modules Management System
GLMM	Generalized linear mixed model
GUI	Guidance
GSK	GlaxoSmithKline
NOT1D	New Onset Type 1 Diabetes Mellitus
PBMC	Peripheral blood mononuclear cell
PCI	Potential Clinical Importance
PDMP	Protocol Deviation Management Plan
PP	Per Protocol
PT	Preferred Term
QC	Quality Control
RAP	Reporting & Analysis Plan
SAC	Statistical Analysis Complete
SAE	Serious Adverse Event
SOC	System Organ Class
TCR / BCR	T-cell Receptor / B-cell Receptor
TFL	Tables, Figures & Listings

10.9.2. Trademarks

Trademarks of the GlaxoSmithKline Group of Companies	Trademarks not owned by the GlaxoSmithKline Group of Companies
NONE	SAS

10.10. Appendix 10: List of Data Displays

10.10.1. Data Display Numbering

The following numbering will be applied for RAP generated displays:

Section	Tables	Figures
Study Population	1.01 to 1.nn	1.01 to 1.nn
Biomarker	2.01 to 2.nn	2.01 to 2.nn
Safety	3.01 to 3.nn	3.01 to 3.nn
Section	Listings	
ICH Listings	1 to x	
Other Listings	y to z	

10.10.2. Mock Example Shell Referencing

Non IDSL specifications will be referenced as indicated and if required an example mock-up displays provided in [Appendix 11: Example Mock Shells for Data Displays](#).

Section	Figure	Table	Listing
Study Population	SP_Fn	SP_Tn	SP_Ln
Biomarker	PD_Fn	PD_Tn	PD_Ln
Safety	SAFE_Fn	SAFE_Tn	SAFE_Ln

NOTES:

- Non-Standard displays are indicated in the 'IDSL / TST ID / Example Shell' or 'Programming Notes' column as '[Non-Standard] + Reference.'

10.10.3. Deliverable [Priority]

Delivery	Description
IA SAC	Interim Analysis Statistical Analysis Complete
SAC	Final Statistical Analysis Complete

10.10.4. Study Population Tables

Study Population Tables					
No.	Population	IDSL / TST ID / Example Shell	Title	Programming Notes	Deliverable [Priority]
Subject Disposition					
1.01	Enrolled	ES1	Summary of Subject Disposition		SAC
1.02	Screened	ES6	Summary of Screen Failures (Screened Subjects Population)		SAC
1.03	Enrolled	NS3	Summary of Subjects by Country and Centre		SAC
Population Analyzed					
1.04	Screened	SP1	Summary of Study Populations		SAC
Demographic and Baseline Characteristics					
1.05	Safety	DM1	Summary of Demographic Characteristics		SAC
1.06	Safety	DM5	Summary of Race and Racial Combinations		SAC
Current and Past Medical Conditions					
1.07	Safety	MH4	Summary of Past Medical Conditions		SAC
1.08	Safety	MH4	Summary of Current Medical Conditions		SAC
Concomitant Medications					
1.09	Safety	CM1	Summary of Concomitant Medications		SAC
Lymph Node Questionnaire					
1.10	Safety	SP_T1	Summary of Pre-Biopsy Lymph Node Questionnaire		SAC
1.11	Safety	SP_T1	Summary of Post-Biopsy Lymph Node Questionnaire		SAC

